## **MACE**

Major Adverse Cardiac Evets (MACE) were defined as one of the following: any death, myocardial infarction, coronary artery bypass grafting

Prior to Screening, MACE are documented on the Relevant medical history CRF, section “Major Adverse Cariac Events”. After start of study drug, MACE are documented on the Adverse Event CRF.

### Death

- Source: Study completion CRF
- Occurrence: “Primary reason for premature discontinuation” = 10 (“Death”)
- Date of event: “Date of death”

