The occurrence of adverse events should be sought by non-directive questioning of the patient at each visit during the study. Adverse events also may be detected when they are volunteered by the patient during or between visits or through physical examination, laboratory test, or other assessments. As far as possible, each adverse event should be evaluated to determine:

1. the severity grade (mild, moderate, severe)
2. its relationship to the study drug (Everolimus) (suspected/not suspected)
3. its duration (start and end dates or if continuing at final exam)
4. action taken i.e:
 - (a) no action taken;
 - (b) study drug dosage adjusted/temporarily interrupted;
 - (c) study drug permanently discontinued due to this adverse event;
 - (d) concomitant medication taken;
 - (e) non-drug therapy given;
 - (f) hospitalization/prolonged hospitalization
5. whether it is serious, where a serious adverse event (SAE) is defined as one which:
 - is fatal or life-threatening
 - results in persistent or significant disability/incapacity
 - constitutes a congenital anomaly/birth defect
 - requires inpatient hospitalization or prolongation of existing hospitalization, unless hospitalization is for:

- routine treatment or monitoring of the studied indication, not associated with any deterioration in condition
- elective or pre-planned treatment for a pre-existing condition that is unrelated to the indication under study and has not worsened since the start of study drug
- treatment on an emergency outpatient basis for an event not fulfilling any of the definitions of a SAE given above and not resulting in hospital admission
- social reasons and respite care in the absence of any deterioration in the patient's general condition
- treatment of acute rejection; acute rejections are considered to be a protocol exempted event. They should not be reported simply because they result in a hospitalization and thus meet the criteria for an SAE.. Acute rejections should be reported as SAEs only if they are unusual in appearance, clinical course and/or are graft threatening
- is medically significant, i.e., defined as an event that jeopardizes the patient or may require medical or surgical intervention to prevent one of the outcomes listed above
- is a MACE or a graft loss

Unlike routine safety assessments, SAEs are monitored continuously and have special reporting requirements; see [Section 8.1](#).

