### **2.7.2 Deaths**

Treatment deaths were summarized together with serious treatment emergent adverse events and other significant treatment emergent adverse events by treatment group for the Safety Set (SAF).

Furthermore, deaths were analyzed as composite part of the secondary endpoints treatment failure and major adverse cardiac events for the Full Analysis Set (FAS).

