#### Loss to follow-up

- Source: Study completion CRF
- Occurrence: “Primary reason for premature discontinuation” = 8 (“Lost to follow-up”)
- Date of event: “Last known date subject took study drug”

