### Myocardial infarction

- Source: Adverse Events CRF
- Occurrence: “Advese event” MedDRA PT in (10000891, 10028596, 10066592, 10049768) AND/OR “Mark if AE meets definition of MACE”=1 (ticked)
- Date of event: “Start date”

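### Death is taken from one reason code on the Study Completion CRF, so a death recorded under another reason always leaves the death component and can leave treatment failure or MACE

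*SAP*

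**What the plan says.** SAP 5.1.3 gives one operational definition of death. The source is the Study Completion CRF, the event is "Primary reason for premature discontinuation” = 10 (“Death", and the date is the date of death. No second source is named.

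Death is used in two composites. SAP 2.7.2 says that "deaths were analyzed as composite part of the secondary endpoints treatment failure and major adverse cardiac events" in the FAS, and SAP 5.1.3 defines MACE as "any death, myocardial infarction, coronary artery bypass grafting". SAP 2.6.2 applies Kaplan-Meier estimation and the log-rank test to each composite and to each of its components, so death is also reported as a result of its own.

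Deaths are recorded on other forms as well. SAP 5.1.3 states: "After start of study drug, MACE are documented on the Adverse Event CRF". Protocol 7.6 makes an event serious if it "is fatal or life-threatening", or if it is a MACE or a graft loss. For safety, SAP 2.7.2 reports that "Treatment deaths were summarized together with serious treatment emergent adverse events".

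Two neighbouring rules in SAP 5.1.3 matter here. Infarction and bypass grafting are each met by listed MedDRA terms and/or by "Mark if AE meets definition of MACE”=1 (ticked", so the tick alone is enough for both. Loss to follow-up, itself a treatment-failure component, is "Primary reason for premature discontinuation” = 8 (“Lost to follow-up" on the same Study Completion field that carries death.

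**The concern.** A field that holds one primary reason can hold death or something else, but not both. The documents leave room for something else:

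- Protocol 7.5 has graft loss reported on the Study Completion CRF, so it can compete with death as the primary reason.
- Protocol 6.5.6 lets the page be completed early for withdrawal of consent or loss to follow-up, while Protocol 7.1 and 8.1 continue SAE collection for 30 days after participation stops. A fatal SAE in that window can fall before Month 18 and after the page has been completed under another reason.
- Protocol 6.5.6 asks for one primary reason and gives death no precedence over the others.

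In such a case the trial database holds a death that the endpoint derivation does not see. Death is the least disputable component of both composites. Losing one can turn an event into a censored observation, or move it to a component where it does not belong.

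**Working it through.** The plan states no figure on this point to reproduce. The check applies the SAP 5.1.3 rules to a randomized patient who dies before Month 18, for each type of completion reason and each state of the MACE box on the adverse event form.

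| Completion reason | MACE box | Death component | Treatment failure | MACE |
|---|---|---|---|---|
| Code 10 (death) | either | counted | counted | counted |
| Code 8 (lost to follow-up) | not ticked | missed | counted, as loss to follow-up | missed (b) |
| Code 8 (lost to follow-up) | ticked | missed | counted, as loss to follow-up | counted, as infarction and bypass |
| Any other | ticked | missed | missed (a) | counted, as infarction and bypass |
| Any other | not ticked | missed | missed (a) | missed (b) |

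(a) Unless the patient also has a qualifying rejection, or a graft loss that the SAP rule picks up. That rule reads graft loss from the Hospitalization CRF, not from the Study Completion CRF.

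(b) Unless the adverse event carries one of the listed infarction or bypass terms.

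Of the four rows without code 10:

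- the death component is missed in 4 of 4;
- treatment failure is missed in 2 of 4, subject to (a);
- MACE is missed in 2 of 4, subject to (b);
- both composites are missed in 1 of 4 (another reason, no tick, no other qualifying event).

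These are counts of rule combinations, not probabilities.

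Dates shift as well. A death kept through code 8 is dated by the last known date of study drug, and a death kept through the MACE tick is dated by the adverse event start date. Neither is the date of death.

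**Scale.** SAP 1.1 gives 162 randomized patients at 1:1. Assuming an even split, 162 / 2 = 81 per arm. One death with no other qualifying event is 1 / 81 = 0.0123, or about 1.2 percentage points of that arm's crude event rate. A smaller FAS would make this slightly larger. The documents give neither the number of deaths nor the number recorded under another reason, so no total effect can be computed.

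**The case against.** The strongest reply is that the situation should be uncommon. The Study Completion CRF has a specific death code and a date-of-death item. Protocol 6.5.6 names death as a reason for completing the page early. Protocol 6.5.5 treats a patient who stops drug as withdrawn only after the Month 18 assessments or once it is clear the patient will not return. Someone who stops drug for an adverse event and dies during follow-up would therefore normally receive code 10. CRF completion instructions, which are not among the documents, may also give death precedence. All of this stands, and it limits how many deaths are exposed.

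There are also safeguards: full verification of SAE documentation (Protocol 9.1), quality control audits before lock (Protocol 9.3) and a narrative for every death (SAP 2.6.2). They make it likely that someone knows of each death. They do not change the derivation rule, which would still leave the death out.

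A reader might infer that any death under another reason is lost from both composites. The documents do not support that. Code 8 and a captured graft loss are themselves treatment failures, and the MACE tick keeps the patient in MACE. A reader might also take a difference between the safety death count and the endpoint death count as proof of an error. It is not: the first concerns treatment deaths in the SAF and the second concerns the FAS, so they can differ with perfect coding. Nor do the documents show that any death was in fact recorded under another reason.

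**Conclusion.** The point holds as a gap in the derivation rule. Death rests on one single-choice field with no stated cross-check. A death recorded under another primary reason is always lost from the death component and can be lost from treatment failure, from MACE, or, in the narrowest case, from both. Where the MACE tick rescues the composite, the components are still wrong, and SAP 1.2 lists MACE and each of its components as a secondary objective.

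The size is about 1.2 percentage points of an arm's crude rate per affected death. This assumes 81 patients per arm and no other qualifying event, and the number of affected deaths is unknown. SAP 2.6.1 treats treatment failure and MACE as exploratory, and the primary GFR analysis does not use this rule. It is a modest point, worth acting on because the remedy is cheap and the component is the hardest one in both composites.

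**What to change.** In SAP 5.1.3, define death as the union of:

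1. Study Completion primary reason Death;
2. any non-missing date of death;
3. any adverse event or SAE documented as fatal. The adverse event items in Protocol 7.6 list no separate fatal-outcome field, so take this from the SAE report or the death narrative if the CRF has none.

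Date the event by the date of death, and count it only within the analysis period, so that a death in the 30 days after Month 18 does not enter. Classify a ticked MACE record that is such a death as death, not as infarction and bypass. Before lock, reconcile the derived deaths with the safety death listing, allowing for the different populations (SAF and FAS) and event windows, and explain any remaining difference.

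The cost is a short program and one reconciliation listing, plus a look at the SAE reports or narratives where the CRF lacks an outcome item. The SAP's document history places it before database lock, so the change would come in time.

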### Myocardial infarction

- Source: Adverse Events CRF
- Occurrence: “Advese event” MedDRA PT in (10000891, 10028596, 10066592, 10049768) AND/OR “Mark if AE meets definition of MACE”=1 (ticked)
- Date of event: “Start date”

### Coronary artery bypass grafting

- Source: Adverse Events CRF
- Occurrence: “Advese event” MedDRA PT = 10011077 AND/OR “Mark if AE meets definition of MACE”=1 (ticked)
- Date of event: “Start date”

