## **1.2 Study objectives and endpoints**

Objectives:

Primary

- Renal function assessed as glomerula filtration rate (GFR) – MDRD formula – 18 months after heart transplantation

Secondary

- To assess occurrence of treatment failures up to or at Month 18 post Tx, while treatment failure is defined as a composite endpoint of biopsy proven acute rejection of ISHLT 1990 grade  $\geq 3A$  (ISHLT 2004 grade  $\geq 2R$ ), acute rejection episodes associated with hemodynamic compromise, graft loss / re-transplant, death, loss to follow-up (at least one condition must be present)

- To assess incidence of MACE and each of its components at Month 18 post Tx
- To assess renal function by GFR – Cockcroft-Gault method – at Month 12 and 18 post Tx
- To assess renal function (serum creatinine) and evolution of renal function between Month 6 and Month 18 post Tx (creatinine slope)
- To assess safety and tolerability at Month 6, 9 and 18 post Tx (acc. to safety parameters specified in section 7.6 of the protocol)

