### **2.6      Analysis of secondary efficacy objective(s)**

#### **2.6.1      Secondary endpoints**

The following secondary efficacy variables were analyzed in an explorative manner:

- Occurrence of treatment failure up to Month 18 defined as composite endpoint of biopsy proven acute rejection of ISHLT 1990 grade  $\geq 3A$  resp. ISHLT 2004 grade  $\geq 2R$ , acute rejection episodes associated with hemodynamic compromise, graft loss / re-transplant, death, loss to follow up (at least one condition must be present).
- Occurrence of MACE and each of its components at Month 18

In addition to the analysis of the primary outcome variable of renal safety and tolerability, the following was analyzed:

- Renal function as assessed by Cockcroft-Gault at month 12 and 18 after Tx
- Serum creatinine and reciprocal creatinine slope (1/serum creatinine versus time) including the treatment period between BL (Month 6) and Month 18

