#### **2.6.2      Statistical hypothesis, model, and method of analysis**

Event data:

Event rates were estimated using the Kaplan-Meier method to handle patients who discontinue the treatment prior to suffering from an event adequately. Time to event was defined as the time from date of randomization to the first documented date of the event. The two groups were compared using the log-rank test.

This procedure was applied for the composite endpoint of treatment failure and each of its components, as well as MACE and each of its components.

Narratives including relevant medical information were provided for each biopsy proven acute rejection, graft loss, or death.

Tolerability:

Analyses of renal function as determined by other calculations (serum creatinine, glomerular filtration rate (GFR, Cockcroft-Gault)) were evaluated in the same manner as described for the primary outcome measure.

The creatinine slope (1 / serum creatinine versus time) was determined from all assessments between Month 6 and Month 18 (both visits included) using a linear regression model. These slopes were compared with a two-sided Wilcoxon ranksum test between the treatment groups.

Additionally, tolerability of study medication was assessed from the rate of patients who withdraw prematurely from study medication or in whom study medication had to be converted to another immunosuppressive regimen due to abnormal laboratory results, adverse events, or toxicity. The frequency distribution of these reasons was presented with absolute and percent values. The most frequent reasons (total  $n \geq 5$ ) for discontinuation and/or conversion as well as the total number of patients who are affected by such intolerance of study medication were compared between the two treatment groups using the exact Fisher test.

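### SAP 5.1.3 lets one untyped MACE tick count as both infarction and bypass, and its graft-loss rule departs from Protocol 7.5 without being declared

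*SAP*

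**What the plan says.** **MACE.** SAP 5.1.3 defines MACE as "any death, myocardial infarction, coronary artery bypass grafting" and states "After start of study drug, MACE are documented on the Adverse Event CRF". The infarction rule is "MedDRA PT in (10000891, 10028596, 10066592, 10049768) AND/OR “Mark if AE meets definition of MACE”=1 (ticked" and the bypass rule is "MedDRA PT = 10011077 AND/OR “Mark if AE meets definition of MACE”=1 (ticked". Both take the start date of the adverse event as the event date. Death is read from the Study Completion form with "Date of event: “Date of death".

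The components matter in their own right. SAP 1.2 lists the objective "To assess incidence of MACE and each of its components at Month 18 post Tx", and SAP 2.6.2, after describing Kaplan-Meier estimation and the log-rank test, adds "This procedure was applied for the composite endpoint of treatment failure and each of its components, as well as MACE and each of its components". SAP 2.6.1 sets the status of these endpoints: "The following secondary efficacy variables were analyzed in an explorative manner".

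**Graft loss.** SAP 5.1.3 finds graft loss through the primary reason recorded on the Hospitalization form and dates it at admission. Protocol 7.5 dates it on the day re-transplantation is scheduled. It has the event reported on the Study Completion form, on the End of Treatment form where medication stops early, and on the SAE form. SAP section 4 declares two changes only: the method for missing primary data and the handling of patients who were not randomized.

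**The concern.** A rule for one component of a composite should pick out that component and nothing else. Here two components share a sufficient condition that carries no event type. If every infarction and bypass is ticked, the two component analyses become identical and neither shows what its title says. Because any death is a MACE and MACE are documented on the adverse event form, a site following the definition could also tick a fatal event. That patient would then appear as an infarction and as a bypass. The composite could also take the start of the adverse event as its event time instead of the date of death.

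The graft-loss rule raises a different risk. A loss that is not the primary reason for an admission is not found. A loss that is found is dated by an event (admission) other than the one the protocol names (scheduling). Graft loss is a component of treatment failure and is analysed separately as well.

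**Working it through.** **1. The MACE rules as a truth table.** Inputs: the two rules in SAP 5.1.3, with AND/OR read as an inclusive or.

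| Adverse event record | Meets infarction rule | Meets bypass rule |
|---|---|---|
| Infarction term, no tick | yes | no |
| Infarction term, tick | yes | yes |
| Bypass term, no tick | no | yes |
| Bypass term, tick | yes | yes |
| Other term (e.g. a fatal event), tick | yes | yes |
| Other term, no tick | no | no |

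Every ticked record meets both rules. If the preferred term alone decides, no record meets both. If term and tick are both required, again no record meets both, but an unticked infarction or bypass is lost.

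**2. Effect of one misassigned patient.** SAP 1.1 gives 162 randomized. Assuming an even split, 162/2 = 81 per arm, and 1/81 = 1.23 percentage points per patient. A smaller full analysis set would make this slightly larger.

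**3. Illustration.** The documents give no event or tick counts, so these are assumptions. CNI-free v CNI, all different patients: infarction 3 v 0, bypass 0 v 1, deaths 2 v 2. There is no other censoring. For the log-rank test, at each event E increases by n₁/N and V by n₁n₂/N², where n₁ and n₂ are the numbers at risk in the CNI-free and CNI arms and N = n₁ + n₂; then χ² = (O − E)²/V on 1 df. For 3 v 0: E = 81/162 + 80/161 + 79/160 = 1.491, V = 0.750, χ² = (3 − 1.491)²/0.750 = 3.04, p = 0.081.

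| What is ticked | Infarction reads | Bypass reads |
|---|---|---|
| Nothing | 3 v 0, p = 0.081 | 0 v 1, p = 0.317 |
| One infarction | 3 v 0, p = 0.081 | 1 v 1, p = 0.996 |
| All infarctions, not the bypass | 3 v 0, p = 0.081 | 3 v 1, p = 0.308–0.317 |
| All infarctions and the bypass | 3 v 1, p = 0.308–0.317 | 3 v 1, p = 0.308–0.317 |
| Those plus one fatal event per arm | 4 v 2, p = 0.395–0.419 | 4 v 2, p = 0.395–0.419 |
| Those plus all fatal events | 5 v 3, p = 0.449–0.491 | 5 v 3, p = 0.449–0.491 |

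Ranges run over all possible event orders; order moves p by at most about 0.04 (0.491 − 0.449). Patients with composite MACE number 3 + 0 + 2 = 5 v 0 + 1 + 2 = 3 in every row. No row crosses 0.05.

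**4. Graft loss side by side.**

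| | Protocol 7.5 | SAP 5.1.3 |
|---|---|---|
| Date | day re-transplantation is scheduled | day of admission |
| Form | End of Treatment (if stopped early), Study Completion, SAE | Hospitalization, primary reason |
| Declared in SAP section 4 | – | no |

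The dates agree only if scheduling and admission fall on the same day. The documents do not allow the effect to be sized.

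**The case against.** Four points can be made on the other side.

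- **The programmer would use the preferred term to separate the components, or the form may hold an event type beside the tick.** Either is possible, since the case report form is not available. But the rule as written uses no such field, and nothing else in the SAP limits the tick.
- **The consequence is small.** This largely stands. The endpoints are exploratory, and the adverse event tables by preferred term (SAP 2.7.1) show infarction and bypass separately. That cross-check is partial: the tables rest on the safety population and leave out events 30 or more days after study medication stopped. The illustration rests on assumed counts. Its row where the bypass comparison changes direction needs sites to tick infarctions but not a bypass, although both are MACE.
- **Protocol 7.5 says where graft loss is reported, not which form the analysis must use.** That is fair for the source. It does not remove the difference in date.
- **The two rejection rules may be in order.** A reader might infer that SAP 5.1.3 loses rejections found on for-cause biopsies, because it names only the visit biopsy form while Protocol 7.5 says results on the Biopsy log / Suspected Rejection form will serve the efficacy analysis. But Protocol 7.5 also has biopsy results recorded on the visit biopsy form, so the SAP follows one of two named sources, and no loss is shown. A reader might also infer that hemodynamic compromise is over-counted, because the SAP uses a yes/no item on the biopsy form with no stated rejection condition where Protocol 7.5 names the Hemodynamic Compromise form. Whether that item is asked only when rejection is present depends on the unseen form. Both are matters to confirm, not demonstrated errors.

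**Conclusion.** The tick rule is wrong as written: under the stated logic every ticked adverse event is both an infarction and a bypass. The graft-loss date differs from Protocol 7.5, and neither that nor the narrower source is declared. Confidence is high on the tick rule and the graft-loss date, and does not extend to the two rejection rules.

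The size of the MACE problem depends on how many events are ticked, and of which kind. A reader might infer that composite MACE is inflated or that a significance conclusion would change. The documents support neither. If only true MACE are ticked, the composite patient count is unchanged, and only its timing can move, when a fatal event is ticked. None of the illustrative scenarios crosses 0.05. With the primary analysis untouched and the endpoints exploratory, this lies between a minor point and one that should be fixed; the low cost of the change favours making it.

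**What to change.** - **MACE.** Use the tick only to identify composite MACE. Assign infarction and bypass by their MedDRA preferred terms, with medical review of ticked events that match neither list; SAP 5.1.3 already uses medical review to classify infections. For fatal events, state that the date of death in the SAP's death rule takes precedence over the start of the adverse event.
- **Graft loss.** Take source and date from Protocol 7.5, or declare and justify the departure in SAP section 4.
- **Confirm against the case report form.** Check that for-cause biopsies reach the biopsy-proven rejection endpoint, and that hemodynamic compromise counts only with a rejection. Add a sentence to SAP 5.1.3 for each.

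The cost is new wording in SAP 5.1.3, and in section 4 if a departure is kept, plus programming. The SAP history places this version before database lock, which is the right time for such a change. The proposed sources are forms the documents already name; whether every needed field is in the database cannot be checked from the documents.
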